## 6 Secondary outcome measures analysis

### 6.1 Longer-term virologic success at Weeks 24, 36 and 48

This outcome measure addresses virologic success rates after completion of the TERA intervention at Week 12, to assess the duration of its effect. The analytic approach will be similar to the primary outcome measure outlined in Section 5, conducting comparisons by arm at Weeks 24, 36 and 48, but with wider allowable windows ( $\pm$ 28 days) around each study visit, and excluding participants who die for reasons unrelated to HIV before each timepoint. If more than one HIV-1 RNA measurement occurs within the allowable 56-day window, the highest value will be chosen. Sensitivity analyses will repeat the primary analysis (i) using observed HIV-1 RNA only (participants with missing week HIV-1 RNA not included in denominator), (ii) using a wider window around the study visit, and (iii) using last observed HIV-1 RNA. An analysis combining data from Weeks 24, 36 and 48 will use generalized linear models to account for the repeated measures for each participant.

## 6.2 Achieving and maintaining virologic success over 48 weeks

This outcome measure is achieving virologic success (HIV-1 RNA < 200 copies/ml) at Week 12 ( $\pm 14$  days) and maintaining virologic suppression through Weeks 24, 36 and 48 (all  $\pm 28$  days). Success rates will be summarized and compared using the same approach as for the primary outcome measure, and excluding participants who die for reasons unrelated to HIV before Week 48.

## 6.3 Adherence

The Electronic Dose Monitoring (EDM) Device will capture whether participants opened the device (and presumably took their designated antiretroviral) and if it was within the allowable window ( $\pm 4$  hours) each day while on study. It is not possible to identify when doses were missed due to EDM functionality, lost or stolen devices, or lack of access to the EDM device due to hospitalization or incarceration. This means that adherence may be under-estimated in each arm. However since these situations should arise equally in the two arms, comparisons between arms should be unbiased.

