## 2 Protocol Overview

### 2.1 Study Design

TERA is a Phase II, randomized, open-label study designed to assess the effectiveness of a Triggered Escalating Real-Time Adherence (TERA) intervention for 12 weeks in Youth Living With HIV (YLWH) failing antiretroviral therapy (ART). This time-limited approach includes education and motivational skills building from an adherence coach and monitoring with wireless electronic dose monitoring (EDM), for identification of delayed and missed doses of antiretrovirals and related alerts and coach phone-based outreach.

The original design was to enroll 120 YLWH, stratify by age (<18 years vs.  $\geq$ 18 years), and randomize with equal probability to TERA or continuing standard-of-care (SOC) for adherence. At entry, half were randomly selected to engage in additional in-depth interviews about their experiences at Weeks 12 and 48, with the goal of having 40 evaluable participants at both time points. Participants were followed for 48 weeks.

In August 2019, the Adolescent Trials Network Safety Monitoring Committee (SMC) recommended that accrual be closed and the 89 enrolled participants continue follow-up to study completion.

In March 2020, study visits were paused due to the outbreak of COVID-19. The study team decided to use the 'pre-COVID' database to analyze the primary and secondary objectives, since data collected after study visits resumed would be inherently different. This required a change to the definition of the virologic secondary outcome measures. It also meant that sample sizes at later study visits would be lower than anticipated, with a corresponding reduction in power to detect differences between arms. Additional data may be collected at study visits that take place after sites re-open. Analysis of these data will be outlined in a separate SAP.

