### 6.3.1 Percent of days with doses taken per week

For each 24-hour window (defined as midnight to midnight), a participant will be classified as having taken their dose if they opened the EDM device, regardless of when in the 24-hour period. For each week (defined as day of study entry (e.g. Monday) plus 6 days (e.g. Sunday)), the percent of days with a dose taken out of days with data in that week will be calculated. These percentages will be summarized across participants in each arm by week and illustrated using a Figure. To address the issue of possible informative censoring of participants lost-to-follow-up for reasons other than death, a second summary will use available data while the participant is on study, and impute 0% for each week after a participant has been lost-to-follow-up and up to the earlier of March 20, 2020 or the date of what would have been their Week 48 study visit. The denominator for the second set of analyses will be the number of participants randomized to each intervention arm with the opportunity of follow-up to each week.

The number of days with a dose taken will be summarized during the intervention phase of the study using interval-censored methods. Participants lost-to-follow-up before 12 weeks will be assigned an interval between the number of doses recorded as taken (minimum possible assuming no further doses taken through full 12 weeks of follow-up) and that number plus the difference between 84 days (12 weeks) and the day they were lost-to-follow-up (maximum possible assuming all further doses taken through full 12 weeks of follow-up). Arms will be compared using a generalized logrank test. Note that this approach is different from the one outlined in the protocol which proposed using repeated measures rank sum tests to compare adherence between arms, as this approach relied on having complete data. A similar approach will be used to summarize adherence in the post-intervention phase (weeks >12 – 48), with the caveat that participants lost-to-follow-up before Week 12 will not be included in post-intervention summaries.

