### 6.3.2 Percent of days with doses taken within defined acceptable windows per week

For each 24-hour window (defined as midnight to midnight), a participant will be classified as having taken their doses on time if they opened the EDM device within the allowable  $\pm 4$  hour window. This outcome will be analyzed in the same way as the outcome in Section 6.3.1. Ability

to determine if the dose was taken 'on time' will depend on the target dose times being correct and updated in real time in the EDM device.

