### **6.3.3 Electronic dose monitored non-persistence**

The outcome measure will be calculated during each 12-week interval (0-12, >12-24, >24-36, >36-48) as the number of 7-day gaps between doses relative to the number of weeks with EDM data reported times 12. This represents an incidence rate (IR) for numbers of gaps of 7 days per 12 weeks on study. For example, each consecutive gap of 7 days will increase the participant's count by one, i.e. missing 20 consecutive days would count as two gaps and missing 22 days would count as three gaps.

Both the number of distinct gaps (regardless of length) and the length of each gap are of interest. The number of participants with at least one gap, the number of gaps regardless of length, and the maximum gap length will be summarized. Incidence rates will be summarized for each 12-week interval and compared within and across the four 12-week intervals by arm using generalized estimating equations with a Poisson link. This analysis does not take into account participants lost-to-follow-up and results will need to be interpreted with caution.

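### Equal device outages would keep the adherence test valid but would not make EDM comparisons unbiased, and Section 6.3 gives no support for equality

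*SAP*

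**What the plan says.** Section 6.3 of the SAP states: "It is not possible to identify when doses were missed due to EDM functionality, lost or stolen devices". It gives loss of access to the device through hospital stays or imprisonment as a further cause. It accepts that adherence may therefore be under-estimated in each arm, and continues: "However since these situations should arise equally in the two arms, comparisons between arms should be unbiased".

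Four other places bear on this:

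- Section 2.1 describes EDM as part of the 12-week TERA approach, "for identification of delayed and missed doses of antiretrovirals and related alerts and coach phone-based outreach".
- Section 6.3.1 defines the weekly measure: "the percent of days with a dose taken out of days with data in that week will be calculated". The between-arm test is a generalized logrank test on the number of days with a dose. Participants lost before week 12 get an interval whose upper limit is "that number plus the difference between 84 days (12 weeks) and the day they were lost-to-follow-up". A similar approach is planned for weeks >12–48.
- Section 6.3.2, on-time doses: "This outcome will be analyzed in the same way as the outcome in Section 6.3.1".
- Section 6.3.3 counts 7-day gaps "relative to the number of weeks with EDM data reported times 12", compares rates by Poisson generalized estimating equations, and adds: "This analysis does not take into account participants lost-to-follow-up and results will need to be interpreted with caution".

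**The concern.** Adherence is the third secondary objective, and Section 6.3 tells the reader how far its between-arm results can be trusted. The argument runs from equal occurrence of outages to unbiased comparison. There are two difficulties.

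First, equal error in two arms protects some quantities and not others. A day on which the device is dead is recorded as a day without a dose, whatever the participant did. This pulls both arms' adherence down by the same proportion, so the absolute gap between them narrows. It can also add the same number of false gaps to both arms, which moves a rate ratio toward 1.

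Second, equality is stated, not shown. The trial is open-label, and in weeks 0–12 the TERA arm has alerts and coach calls driven by the device signal. A silent device might be noticed at a different time in the two arms. Randomization balances participants at entry; it does not ensure that devices are followed up alike afterwards.

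At stake is interpretation: an attenuated difference could be read as the true size, or a difference in outages as a difference in adherence.

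**Working it through.** **Inputs.** From the SAP: 84 days in the intervention phase (6.3.1), 89 enrolled with equal allocation (2.1), and consecutive missed time counted in 7-day units (6.3.3). The SAP gives no adherence level or outage rate, so there is no figure to reproduce. Assumed: true adherence 70% v 50%, or 60% in both arms for no difference; outage share f of 5, 10 or 20% of days, independent of dosing.

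**Step 1: equal outage, days with a dose.** Recorded adherence = p(1−f), so the difference is (pT − pS)(1−f) and the ratio is pT/pS.

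| f | Difference, points | Difference, days of 84 | Ratio |
|---|---|---|---|
| 0 | 20 | 16.8 | 1.40 |
| 5% | 20 × 0.95 = 19 | 16.0 | 1.40 |
| 10% | 20 × 0.90 = 18 | 15.1 | 1.40 |
| 20% | 20 × 0.80 = 16 | 13.4 | 1.40 |

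**Step 2: equal outage, gap rate.** If each outage week counts as one gap and stays in the denominator, the recorded rate per 12 weeks is 12f + (1−f)r. With r = 1 v 2 (true ratio 0.50):

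- f = 5%: (0.60 + 0.95)/(0.60 + 1.90) = 1.55/2.50 = 0.62
- f = 10%: (1.20 + 0.90)/(1.20 + 1.80) = 2.10/3.00 = 0.70
- f = 20%: (2.40 + 0.80)/(2.40 + 1.60) = 3.20/4.00 = 0.80

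Across base rates from 0.5 v 1 to 2 v 4, the ratios are 0.57–0.69, 0.63–0.79 and 0.71–0.88. If outage weeks leave both numerator and denominator, the ratio stays 0.50.

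**Step 3: unequal outage, no true difference.** Recorded difference = p(f2 − f1). With p = 60% and 5% v 10%: 57 − 54 = 3 points, or 2.5 of 84 days, in whichever direction the outages differ.

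**Step 4: the test.** Logrank test on days with a dose was simulated with 44 v 45 participants, beta-binomial days, between-participant SD 25–35 points and 10,000 runs per setting. Outages were one 28-day block, one 14-day block (not possible at f = 20%) or scattered days.

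| Setting | Rejection rate |
|---|---|
| No true difference, no outage | 5.2–5.6% |
| No true difference, equal 5–20% | 4.9–5.8% |
| No true difference, 5% v 10%, 28-day blocks | 7.9–9.3% |
| No true difference, 5% v 10%, 14-day blocks | 12.4–13.7% |
| No true difference, 5% v 10%, scattered days | 17.1–33.1% |
| 70% v 50%, no outage | 92.1–97.6% |
| 70% v 50%, equal 5% | 85.4–96.9% |
| 70% v 50%, equal 10% | 82.4–96.5% |
| 70% v 50%, equal 20% | 75.6–95.9% |

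The scattered-day row deserves little weight: loss, theft, hospital stays and imprisonment produce runs of silent days.

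**Step 5: does later text repair this?** Compare two participants with 40 recorded doses. One is lost at day 56 and gets the interval 40 to 40 + (84 − 56) = 68. The other stays on study for 84 days with a device dead for 28 of them and gets exactly 40. The same silent time is treated as unknown in one case and as non-adherence in the other. Section 6.3.2 inherits the rule, and the caution in 6.3.3 names only loss to follow-up. The denominators in 6.3.1 and 6.3.3 refer to days or weeks with data, but the SAP does not say whether silent time qualifies. Its own remark that adherence may be under-estimated suggests that outage days are counted.

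**The case against.** The strongest reply is that, under the SAP's premise, the planned test is sound. The only test specified for days with a dose is a null test, its error rate stays near 5% under equal outage, and no absolute adherence difference with a confidence interval is planned. That stands: under equality the cost is attenuated size and some power, not false positives. It does not cover the arm summaries from which a reader takes the size of the effect, or the gap-rate comparison in 6.3.3.

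The SAP also hedges its wording, discloses under-estimation in each arm, and in Section 4.1 asks for caution with p-values. But the disclosure concerns levels, and the sentence at issue then reassures on comparisons.

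A reader might infer that TERA's alerts make outages shorter in that arm and so flatter TERA in weeks 0–12. The document does not support that. Section 2.1 speaks of delayed and missed doses, not device repair, and the SAP does not say how SOC devices are checked. A coach's call would not shorten a hospital stay. Unequal outage is a possibility that the SAP neither shows nor excludes.

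Finally, Section 7 lists data completeness as a report component and leaves detail to the Analysis Implementation Plan, which is not at hand. It may define the denominators or tabulate outages. It would not correct the sentence in Section 6.3.

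**Conclusion.** The reassurance in Section 6.3 should be narrowed. If outages are equal and independent of dosing, the test of no difference is valid and the ratio of mean adherence is preserved. Absolute differences still shrink by (1−f), 1 to 4 points out of 20 for assumed outages of 5–20%, when outage days count as missed. Under the conditions of Step 2, a gap-rate ratio of 0.50 moves to 0.62–0.80. If outages are unequal, the comparison can be biased in either direction: 5% v 10% gives a spurious 3 points at 60% adherence, and error rates of about 8–14% for outages in blocks.

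All of these sizes rest on assumed rates and patterns. They do not show that the adherence comparison is invalid or that it favours either arm. The point affects what may be concluded from the third secondary objective; the primary HIV-1 RNA outcome is untouched.

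**What to change.** Three changes to Section 6.3:

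1. Replace the sentence with: *If such failures are equal and independent of dosing, the test of no difference remains valid but absolute differences and gap-rate ratios may be attenuated; if they are unequal, comparisons may be biased in either direction.*
2. Report by arm, for weeks 0–12 and >12–48, the number and length of silent runs of at least 7 days (the SAP's own gap length), with any device loss, malfunction or no-access periods already recorded.
3. Add a sensitivity analysis applied to both arms alike. Treat periods with a recorded outage as interval-censored in 6.3.1 and 6.3.2, as loss to follow-up already is, and remove them from both the gap count and the weeks denominator in 6.3.3.

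Restrict the third change to recorded outages. Censoring every long silent run would censor on the SAP's own non-persistence outcome. Doing so in one arm only gave 7–12% rejection with no outage and no true difference (300 runs, Monte Carlo error about 2–5 points).

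The cost is one sentence, one table and one rerun of planned analyses on data already held, with no new collection. The adherence conclusion will be more cautious, and unrecorded outages will remain uncorrected.

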### 6.3.1 Percent of days with doses taken per week

For each 24-hour window (defined as midnight to midnight), a participant will be classified as having taken their dose if they opened the EDM device, regardless of when in the 24-hour period. For each week (defined as day of study entry (e.g. Monday) plus 6 days (e.g. Sunday)), the percent of days with a dose taken out of days with data in that week will be calculated. These percentages will be summarized across participants in each arm by week and illustrated using a Figure. To address the issue of possible informative censoring of participants lost-to-follow-up for reasons other than death, a second summary will use available data while the participant is on study, and impute 0% for each week after a participant has been lost-to-follow-up and up to the earlier of March 20, 2020 or the date of what would have been their Week 48 study visit. The denominator for the second set of analyses will be the number of participants randomized to each intervention arm with the opportunity of follow-up to each week.

The number of days with a dose taken will be summarized during the intervention phase of the study using interval-censored methods. Participants lost-to-follow-up before 12 weeks will be assigned an interval between the number of doses recorded as taken (minimum possible assuming no further doses taken through full 12 weeks of follow-up) and that number plus the difference between 84 days (12 weeks) and the day they were lost-to-follow-up (maximum possible assuming all further doses taken through full 12 weeks of follow-up). Arms will be compared using a generalized logrank test. Note that this approach is different from the one outlined in the protocol which proposed using repeated measures rank sum tests to compare adherence between arms, as this approach relied on having complete data. A similar approach will be used to summarize adherence in the post-intervention phase (weeks >12 – 48), with the caveat that participants lost-to-follow-up before Week 12 will not be included in post-intervention summaries.

### 6.3.2 Percent of days with doses taken within defined acceptable windows per week

For each 24-hour window (defined as midnight to midnight), a participant will be classified as having taken their doses on time if they opened the EDM device within the allowable  $\pm 4$  hour window. This outcome will be analyzed in the same way as the outcome in Section 6.3.1. Ability

to determine if the dose was taken 'on time' will depend on the target dose times being correct and updated in real time in the EDM device.

### **6.3.3 Electronic dose monitored non-persistence**

The outcome measure will be calculated during each 12-week interval (0-12, >12-24, >24-36, >36-48) as the number of 7-day gaps between doses relative to the number of weeks with EDM data reported times 12. This represents an incidence rate (IR) for numbers of gaps of 7 days per 12 weeks on study. For example, each consecutive gap of 7 days will increase the participant's count by one, i.e. missing 20 consecutive days would count as two gaps and missing 22 days would count as three gaps.

Both the number of distinct gaps (regardless of length) and the length of each gap are of interest. The number of participants with at least one gap, the number of gaps regardless of length, and the maximum gap length will be summarized. Incidence rates will be summarized for each 12-week interval and compared within and across the four 12-week intervals by arm using generalized estimating equations with a Poisson link. This analysis does not take into account participants lost-to-follow-up and results will need to be interpreted with caution.

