24 ( $\pm$  28 days) and Week 36 ( $\pm$  28 days) HIV-1 RNA measurements is < 200 copies/mL. Participants will be classified as failures if (1) either of the Week 12 or 48 HIV-1 RNA measurements are  $\geq$  200 copies/mL, (2) HIV-1 RNA at both Week 24 ( $\pm$  28 days) and Week 36 ( $\pm$  28 days) are  $\geq$  200 copies/mL, (3) both the HIV-1 RNA measurements between Weeks 12 and 48 are missing, or (4) either or both the Week 12 and Week 48 HIV-1 RNA are missing.

3. To summarize and compare adherence patterns in YLWH initiating TERA or continuing SOC during on-intervention period (week 0-12) and post intervention period (week >12-48).

Outcome measures:

- i. Electronic dose monitored adherence: Percent of days with dose taken per week
- ii. Electronic dose monitored on-time adherence: Percent of days with dose taken within the defined acceptable windows ( $\pm$  4 hours) per week.
- iii. Electronic dose monitored non-persistence: Number of gaps (at least 7 consecutive days (168 hours) between doses) in the intervals: week 0-12, >12-24, >24-36 and >36-48.

## 5 Primary outcome measure analysis: short term virologic success at Week 12

The primary objective of the study is to estimate and compare HIV virologic suppression rates (HIV-1 RNA < 50 copies/ml and <200 copies/ml) 12 weeks after initiating the TERA intervention or continuing SOC. If more than one HIV-1 RNA measurement occurs within the allowable 28-day window, the highest value will be chosen. Other than participants dying for reasons unrelated to HIV before Week 12, all eligible participants will be included in this analysis, classifying those lost-to-follow-up as failures. Sensitivity analyses will repeat the primary analysis (i) using observed HIV-1 RNA only (participants with missing week 12 HIV-1 RNA not included in denominator), (ii) using a wider window around the Week 12 study visit, and (iii) using last observed HIV-1 RNA if missing week 12.

Virologic success rates in each arm and the difference in success rates between arms will be summarized with 95% confidence intervals (CIs). Analyses adjusting for covariates identified *a priori* by the study team will be conducted to assess whether the magnitude and strength of the association between the intervention and virologic success changes after adjustment for other factors.

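### SAP 6.3.3 leaves lapses that end in loss to follow-up (and, read literally, any lapse with no later dose) out of the non-persistence rate, so a difference between arms in permanent stopping can be hidden or distorted

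*SAP*

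**What the plan says.** **Numerator.** SAP 6.3.3 defines the outcome in each 12-week interval "as the number of 7-day gaps between doses". SAP 4.3 has the same element: "Number of gaps (at least 7 consecutive days (168 hours) between doses". The worked example in 6.3.3 counts in 7-day units: "missing 20 consecutive days would count as two gaps and missing 22 days would count as three gaps".

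**Denominator.** The count is taken "relative to the number of weeks with EDM data reported times 12". The next sentence reads: "This represents an incidence rate (IR) for numbers of gaps of 7 days per 12 weeks on study". The SAP does not say whether an on-study week without an opening is a week with data.

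**Loss to follow-up.** Section 6.3.3 ends: "This analysis does not take into account participants lost-to-follow-up and results will need to be interpreted with caution". For the sister outcome, 6.3.1 names possible informative censoring. It plans a second summary that will "impute 0% for each week after a participant has been lost-to-follow-up", up to the earlier of March 20, 2020 or the would-be Week 48 date and only for loss other than by death. It also plans an interval-censored analysis of days with a dose. Section 6.3.2 is analysed in the same way. Section 6.3.3 has no counterpart.

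**The concern.** Persistence means staying on treatment, so participants who stop and do not return are the most informative cases. A count of gaps closed by a later dose records those who lapse and come back, and misses those who lapse and leave. Stating that lost participants are ignored discloses the problem but neither bounds nor corrects it.

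The comparison between arms is at stake. SAP 2.1 describes alerts and coach outreach for missed doses in the TERA arm. Outreach could plausibly bring more lapses to a close in that arm. A closed lapse is counted and an open one may not be, so the measure could treat the arms unequally. The SAP gives no figures on this; it is a mechanism, not a finding.

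A lesser matter is that the formula and its label name two time bases, and these agree only if silent on-study weeks count as data.

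**Working it through.** **Inputs from the SAP.** Intervals of 12 weeks (84 days); 7-day counting units; rate = count ÷ weeks × 12 (6.3.3). Participant profiles and arm-level rates below are assumptions, because the SAP gives none.

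**1. The plan's own example.** Count = floor(missed days ÷ 7). For 20 days: 20/7 = 2.86, so 2. For 22 days: 22/7 = 3.14, so 3. Both match 6.3.3. If the 168 hours between doses of 4.3 is used as the unit, with one dose a day, 20 missed days put 21 days (504 hours = 3 × 168) between doses and give 3, not 2. The two sections should be reconciled.

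**2. Stopping for good, no earlier gap, last dose at the end of week w.** Under the literal reading there is no closing dose, so the count is 0 and the rate is 0 whether the denominator is w or 12. Counted to the end of the interval, the lapse has (84 − 7w)/7 = 12 − w units over 12 weeks.

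| Stop after week | Literal reading | Lapse counted, per 12 weeks |
|---|---|---|
| 4 | 0/4 × 12 = 0 | 8/12 × 12 = 8.0 |
| 8 | 0/8 × 12 = 0 | 4/12 × 12 = 4.0 |

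Zero is not general. With an earlier closed 14-day gap and a stop after week 8, the literal rate is 2/8 × 12 = 3.0 (2/6 × 12 = 4.0 if silent weeks are dropped), against (2 + 4)/12 × 12 = 6.0 with the final lapse counted. A later interval with no data gives 0/0, so the participant drops out of it.

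**3. Denominator, for a participant who returns after three silent weeks.** If silent weeks are data: 3/12 × 12 = 3.0. If they are not: 3/9 × 12 = 4.0. A 22-day lapse can also leave 10 weeks with an opening, depending on alignment: 3/10 × 12 = 3.6. Section 6.3.1 bears on which reading is meant: "the percent of days with a dose taken out of days with data in that week will be calculated". If only days with an opening were data, that percentage would always be 100%, so a day without an opening must be able to count as data.

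**4. Arm level, assumed inputs.**

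*Case A:* 1.5 gaps per 12 weeks while observed, in everyone; loss at week 6. A lost participant has 0.75 gaps before loss and, if time after loss counts as non-use, 6 more: 6.75.
- As written: 1.5 at any level of loss.
- Counted, 5% lost: 0.95 × 1.5 + 0.05 × 6.75 = 1.76.
- Counted, 25% lost: 0.75 × 1.5 + 0.25 × 6.75 = 2.81.
- Ratio of the two arms: 1.00 as written, 2.81/1.76 = 1.60 when counted.

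*Case B:* 0.5 gaps per 12 weeks in those who stay; stoppers leave after week 4 without an earlier gap.
- As written, 10% stoppers: 0.45/(0.9 × 12 + 0.1 × 4) × 12 = 0.48.
- As written, 30% stoppers: 0.35/(0.7 × 12 + 0.3 × 4) × 12 = 0.44.
- Counted: 0.45 + 0.1 × 8 = 1.25 and 0.35 + 0.3 × 8 = 2.75.

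In neither case does the rate as written register the extra stopping.

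**The case against.** The limitation is stated openly, and this is the third measure under a secondary objective of a Phase II study. A rate over observed time is a common choice. SAP 1.1 leaves coding descriptions to the Analysis Implementation Plan, which is not at hand and may define the terms. All of this is fair and bears on priority. It does not supply the missing analysis: the exclusion stands in the SAP itself, and the SAP treats the same problem as worth two remedies in 6.3.1.

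Three stronger readings are tempting, and the documents do not support them.

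- *The rate is inflated in those who lapse and return.* This needs silent weeks not to be data. The phrase in 6.3.1, the statement in 6.3 that misses caused by device problems cannot be identified and may lower measured adherence, and the on-study label in 6.3.3 all favour a 12-week denominator. What stands is a conflict of wording.
- *Everyone who stops for good scores zero.* Earlier closed gaps still count, later empty intervals drop out, and the example of missed days mentions no closing dose, so a final lapse while still on study might be counted. Only loss to follow-up is expressly left out.
- *The rate ratio points the wrong way.* Case A shows a masked difference, not a reversed one. The small downward drift in case B comes from assuming that stoppers had no earlier gap. The SAP gives neither loss by arm nor a gap rate, so no direction can be claimed for this trial.

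**Conclusion.** The point holds in this form. Lapses that end in loss to follow-up are left out by the SAP's own statement, and the requirement that a gap lie between doses leaves out, on a literal reading, any lapse never closed. For one participant with no earlier gap, this is 0 against 8 per 12 weeks for a stop after week 4, and 0 against 4 for a stop after week 8. At arm level, a difference in permanent stopping can be hidden or distorted; the size depends on loss by arm and on drug use after loss, and the figures above are illustrations under stated assumptions. If stopping is alike in both arms and preceded by similar gap rates, the comparison suffers less, although the level is still too low wherever lapses go uncounted.

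The denominator is mainly a wording conflict. It would change a result (4.0 instead of 3.0 for three silent weeks) only on the less likely reading.

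**What to change.** In SAP 6.3.3:

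1. Use on-study weeks in each interval as the exposure, entered as a log offset in the Poisson model. This matches the section's own label and settles whether silent weeks count.
2. Count an unclosed lapse in 7-day units up to the participant's last on-study day in the interval.
3. Add a sensitivity analysis with the rule of 6.3.1: time after loss to follow-up for reasons other than death counts as non-use, up to the earliest of the interval end, March 20, 2020 or the would-be Week 48 date. Time after death is not counted.
4. Reconcile the 168-hour definition in 4.3 with the example of missed days.

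The cost is a few sentences and a small programming change. If the analysis has begun, SAP 4.1 requires the change to be identified as post hoc.

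There are two downsides. The sensitivity analysis overstates gaps if lost participants kept taking ART, so it belongs beside the main result and does not replace it. On-study silence caused by a lost device or a hospital stay counts as non-use, which 6.3 already accepts for the adherence outcomes.

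### The non-persistence outcome defined in SAP 4.3 is not the rate compared in 6.3.3, and the midnight cut in 6.3.2 can score an on-time dose as not on time (secondary adherence outcomes only)

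*SAP*

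**What the plan says.** **Non-persistence.** SAP 4.3, under secondary objective 3, gives the outcome as "Number of gaps (at least 7 consecutive days (168 hours) between doses", counted in each of four 12-week intervals. SAP 6.3.3 calculates it "as the number of 7-day gaps between doses relative to the number of weeks with EDM data reported times 12". Under its counting rule "each consecutive gap of 7 days will increase" the participant's count by one, with the example that "missing 20 consecutive days would count as two gaps and missing 22 days would count as three gaps". The same section takes a separate interest in distinct gaps: "the number of gaps regardless of length, and the maximum gap length will be summarized". The between-arm comparison is confined to the rate: "Incidence rates will be summarized for each 12-week interval and compared within and across the four 12-week intervals by arm", by generalized estimating equations.

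**On-time adherence.** SAP 6.3.2 states: "For each 24-hour window (defined as midnight to midnight), a participant will be classified as having taken their doses on time" if the device was opened within 4 hours either side of the target. SAP 6.3.1 uses the same calendar day for any-time adherence. SAP 6.3 adds that the device captures whether it was opened "and if it was within the allowable window" each day. SAP 1.1 leaves coding descriptions to a separate Analysis Implementation Plan (AIP).

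**The concern.** Section 4.3 is where a reader looks for the definition of an outcome, and SAP 1.1 says the report built on this plan supplies the results posted to ClinicalTrials.gov. If the posted definition is the 4.3 count and the posted comparison is the 6.3.3 rate, the result carries the wrong description. The two quantities answer different questions. The 4.3 count measures how often participants lapse, while the 6.3.3 rate also weights each lapse by its length.

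The unit matters for the same reason. Section 4.3 speaks of hours between doses and the 6.3.3 example speaks of days missed, and these are one day apart for a once-daily regimen. Two programmers could follow the text and obtain different counts.

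The on-time rule has a different fault. A window of ±4 hours around a late-evening or early-morning target does not fit inside one calendar day, so a dose taken within the window can land on the wrong date.

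**Working it through.** **Inputs.** Gap threshold of 7 days or 168 hours (4.3); one added per 7-day block, and the 20- and 22-day example (6.3.3); window of ±4 hours (4.3, 6.3.2); calendar-day scoring (6.3.1, 6.3.2). Once-daily dosing is an assumption, supported by the removal of BID regimens (1.2) and by the one-dose-per-day scoring in 6.3.1. A constant dosing time is a further assumption for the conversion to hours.

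**Step 1: the SAP's own example.** Taken as missed days, floor(20/7) = 2 and floor(22/7) = 3. The example is reproduced.

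**Step 2: count, same unit in both sections.** For a lapse of L days, closed by a dose at each end, the 4.3 count is 1 if L ≥ 7 and otherwise 0. The 6.3.3 count is floor(L/7).

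| Lapse (days) | 4.3 | 6.3.3 |
|---|---|---|
| 7 to 13 | 1 | 1 |
| 14 to 20 | 1 | 2 |
| 21 to 27 | 1 | 3 |
| 28 | 1 | 4 |

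The counts agree up to 13 days and differ at every length from 14 on. With 12 full weeks of data, a 20-day lapse gives a rate of 2/12 × 12 = 2.0 under 6.3.3, against 1/12 × 12 = 1.0 if it counts once. As an illustration only, compare a participant with four separate 7-day lapses to one with a single 28-day lapse. The counts are 4 and 1 under 4.3, but 4 and 4 under 6.3.3.

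**Step 3: unit.** At a constant once-daily time, n missed days leave (n + 1) × 24 hours between doses.

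- n = 6: 7 × 24 = 168 hours. This is a gap by 4.3 and none by missed days.
- n = 20: 21 × 24 = 504 hours, and 504/168 = 3 blocks. The 6.3.3 example says two.
- n = 22: 23 × 24 = 552 hours, and floor(552/168) = 3 blocks. The example also says three.

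Under the splitting rule, missed days and hours give different counts at 6, 13, 20, 27, … missed days, that is, at every seventh length. Read literally, the 20-day example fits missed days and does not fit 168-hour blocks.

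**Step 4: on-time window.** For a target at clock hour T, the part of the 8-hour window on another date is (T + 4 − 24)/8 for late targets and (4 − T)/8 for early ones. At 20:00 or 04:00 it is 0. At 22:00 it is (22 + 4 − 24)/8 = 25%, and at 02:00 it is (4 − 2)/8 = 25%.

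Take a 22:00 target with openings on day 1 at 22:00, day 3 at 01:00 and day 3 at 22:00. The 01:00 opening is 3 hours after the day 2 target and so on time. Day 2 nevertheless has no opening on its own date and is scored not on time. If the rest of the week is on time, the week scores 6/7 = 85.7% instead of 100%.

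**The case against.** **Section 4.3 is only a short list, and 6.3.3 is the operative definition.** This is partly right. Section 6.3.3 gives the denominator, the splitting rule, an example and the model, and it reports distinct gaps and maximum length as well. A reader might infer that the plan leaves open which count is tested. It does not: 6.3.3 is clear that the rate is compared, and no quantity is lost. Section 4.3 also gives no explicit rule for long lapses; that one lapse is one gap follows from its setting a minimum length and no maximum. What remains is that 6.3.3 itself separates distinct gaps from the split count, and the one that 4.3 describes is the one that is only summarized.

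**The example can be reconciled with hours.** If the 20 and 22 days are reread as elapsed days between doses, floor(480/168) = 2 and floor(528/168) = 3, and the example fits. But the example speaks of missing days, and in that literal sense it conflicts with 168 hours. That a reader must reinterpret it is reason enough to rewrite it.

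**The midnight problem may be small or handled elsewhere.** This stands as a limit on its size. The device may flag on-time openings itself, and the AIP is not at hand. A participant who regularly opens just after midnight still has one opening on each date, so with a device flag the loss need not accumulate. The 25% is a share of the window, and a reader might wrongly take it as a share of doses misclassified. Even so, the rule written in 6.3.2 is the calendar-day one, and in the example above a device flag does not give day 2 an opening.

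**Conclusion.** The point holds and is minor. The outcome defined in 4.3 and the rate compared in 6.3.3 are different quantities for every lapse of 14 days or more. The 168-hour unit of 4.3 conflicts with the literal missed-day example in 6.3.3, given once-daily dosing at a constant time. The calendar-day rule in 6.3.2 can score an on-time dose as not on time when the target is after 20:00 or before 04:00.

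A reader might go further and infer that the arm comparisons are biased. The SAP does not support that. It gives no expected lapse lengths and no target times, so neither the size nor the direction of any effect by arm can be derived. Only the secondary adherence outcomes are touched; the virologic outcomes, including the primary one, do not use these rules.

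**What to change.** 1. In 4.3, state that the compared non-persistence outcome is the 7-day-block incidence rate of 6.3.3, and that distinct gaps of any length are descriptive.
2. Choose one unit, missed days or elapsed hours between openings, and use it in 4.3, in 6.3.3 and in the worked example.
3. Define the dosing day around the target time, for example target ±12 hours, and assign each opening to that day in both 6.3.1 and 6.3.2. Changing 6.3.2 alone would create a new inconsistency. In the example week, on-time adherence would be 7/7 while any-time adherence stayed at 6/7, although on-time days must be a subset of days with a dose taken.

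The cost is a few sentences in 4.3, 6.3.1 and 6.3.2, a reworded example in 6.3.3, and some extra programming on data already time-stamped. No new data are needed, and the primary outcome is unchanged.
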